4.6 End of Study

The end of the study is defined as the date of the last visit of the last patient taking part in the study.

4.7 Study Discontinuation by the Sponsor

For reasonable cause, either the Investigator or the Sponsor may terminate this study prematurely. Written notification of the termination is required. Conditions that warrant termination by the Sponsor include, but are not limited to:

- The discovery of an unexpected, significant, or unacceptable risk to the patients enrolled in the study.
- Failure of the Investigator to enter patients at an acceptable rate.
- Insufficient adherence to protocol requirements (non-compliance).

- Lack of evaluable and/or complete data.
- Decision to modify the developmental plan of the drug.
- A decision on the part of the Sponsor to suspend or discontinue development of the drug.

4.8 Treatment Plan for Patients after the Study

It is expected that patients will go on to receive treatment according to usual hospital practice.

5.0 SELECTION AND WITHDRAWAL OF PATIENTS

5.1 Inclusion Criteria

To be eligible to participate in this study, patients must meet all of the following inclusion criteria:

1. Archived sections from the original formalin fixed paraffin embedded sample reviewed by a gynecological pathologist confirming HGSOE, high grade serous peritoneal cancer or primary fallopian tube cancer and positive immunohistochemistry staining for p53 assessed according to the local methodology (as detailed in the laboratory manual). Cases that do not show p53 staining will not be included.
2. Disease progression between 4 weeks and 6 months after the last platinum-based treatment was administered.
3. At least a single (RECIST 1.1) measurable lesion.
4. Adequate organ function prior to registration:
 - a) Bone marrow reserve
 - Absolute neutrophil count (ANC) $\geq 1.5 \times 10^9/L$
 - Platelets $\geq 100 \times 10^9/L$
 - Hemoglobin ≥ 9 g/dL
 - b) Hepatic
 - Total bilirubin level $< 1.5 \times$ upper limit of normal (ULN) without hepatic metastasis, and $< 4 \times$ ULN with hepatic metastasis
 - Alanine aminotransferase (ALT) and aspartate aminotransferase (AST) $< 2.5 \times$ ULN without hepatic metastasis, and $< 4 \times$ ULN with hepatic metastasis
 - c) Renal
 - Calculated creatinine clearance > 30 mL/min calculated per local practice
 - d) Electrolytes
 - Potassium within institutional normal ranges.
5. Toxicities from previous cancer therapies (excluding alopecia) must have recovered to grade 1 (defined by National Cancer Institute [NCI] Common Terminology Criteria for Adverse Events [CTCAE] version 4.0). Chronic stable grade 2 peripheral neuropathy secondary to neurotoxicity from prior therapies may be considered on a case by case basis by the Principal Investigator.
6. If of childbearing potential, negative pretreatment serum pregnancy test.
7. If of childbearing potential, willing to use an effective form of contraception (see below)

during chemotherapy treatment and for at least 6 months thereafter. Such methods include the following (if using hormonal contraception, this method must be supplemented with a barrier method, preferably male condom):

- combined (estrogen and progestogen containing) hormonal contraception associated with inhibition of ovulation:
 - oral
 - intravaginal
 - transdermal
 - progestogen-only hormonal contraception associated with inhibition of ovulation:
 - oral
 - injectable
 - implantable
 - intrauterine device (IUD)
 - intrauterine hormone-releasing system (IUS)
 - bilateral tubal occlusion
 - vasectomized partner
 - true sexual abstinence when this is in line with the preferred and usual lifestyle of the subject. Periodic abstinence (e.g., calendar, ovulation, symptothermal, post-ovulation methods), declaration of abstinence for the duration of a trial, and withdrawal are not acceptable methods of contraception.
8. Eastern Cooperative Oncology Group (ECOG) performance status of 0 to 2 (Appendix I).
 9. ≥ 18 years of age.
 10. Signed informed consent.

5.2 Exclusion Criteria

1. Prior exposure to cumulative doses of doxorubicin >400 mg/m² or epirubicin >720 mg/m².
2. Confirmed cardiac history of any of the following:
 - a) A myocardial infarct within 6 months prior to registration,
 - b) New York Heart Association Class II or worse heart failure (Appendix II)
 - c) A history of familial long QT syndrome
 - d) Clinically significant pericardial disease

- e) Electrocardiographic evidence of acute ischemia
 - f) Symptomatic atrial or ventricular arrhythmias not controlled by medications
 - g) QTc \geq 480 msec calculated from a single electrocardiogram (ECG) reading or a mean of three ECG readings using Fridericia's correction ($QTcF = QT/RR^{0.33}$)
 - h) Bradycardia (< 40 bpm)
 - i) Left ventricular ejection fraction (LVEF) < the institution lower limit of normal as assessed by echocardiogram (ECHO).
3. Major abdominal surgery or peritonitis within 6 weeks prior to study treatment.
 4. Unresolved bowel obstruction, subocclusive disease or the presence of brain metastases.
 5. Hypersensitivity to PLD or to any of the excipients.
 6. Unable to undergo imaging by either computed tomography (CT) scan or magnetic resonance imaging (MRI).
 7. Evidence of any other medical conditions (such as psychiatric illness, infectious diseases, neurological conditions, physical examination or laboratory findings) that may interfere with the planned treatment, affect patient compliance or place the patient at high risk from treatment related complications.
 8. Breast feeding.
 9. Concurrent malignancy requiring therapy (excluding non-invasive carcinoma or carcinoma in situ).
 10. Known HIV positive status, active hepatitis B or C status.
 11. Is taking any concurrent (or within 4 weeks prior to registration) anti-cancer therapy, immunotherapy, radiotherapy, ancillary anti-cancer therapy, or any therapy that is considered to be investigational (i.e., used for non-approved indications(s) and in the context of a research investigation). Supportive care measures are allowed. Palliative limited radiation therapy for pain reduction is allowed.

5.3 Withdrawal of Patients and Study Termination

In accordance with the Declaration of Helsinki, each patient is free to withdraw from the study at any time without penalty or loss of benefits or other adequate treatments to which he/she is otherwise entitled.

Investigators also have the right to withdraw patients from the study in the event of illness, AEs, or other reasons concerning the health or well-being of the patient, or in the case of lack of co-operation. After withdrawal of a patient, the investigator is responsible for ensuring adequate treatment and follow-up, although every effort should be made to complete all assessments at an end-of-treatment visit as listed in Section 7.2.5.

Should a patient decide to withdraw after administration of the IMP, or should the investigators decide to withdraw the patient, all efforts will be made to complete and report the observations up to the time of withdrawal as thoroughly as possible. A complete final evaluation at the time of the patient's withdrawal should be made and an explanation given of why the patient is withdrawing or being withdrawn from the study.

The reason, time and date for withdrawal must be noted in the eCRF. If the reason for withdrawal is a clinical AE, monitoring will continue until the outcome is evident. The specific event must be recorded in the eCRF.

Patients who are withdrawn before completion of the first cycle of APR-246 and PLD as prescribed will be replaced.

The study treatment with APR-246 will be discontinued if any of the following situations occur (in the case of study termination by the Sponsor, patients will be allowed to continue to receive the standard of care):

1. Progressive disease per RECIST 1.1 criteria.
2. The development of toxicity which precludes further study treatment.
3. Patient refusal.
4. Lost to follow-up/noncompliance.
5. Significant illness that can affect the patient's ability to comply with study procedures.
6. At the discretion of the Investigator.
7. Pregnancy.
8. Study termination by Sponsor.

5.4 Compliance with Study Procedures

Patients will receive the study treatment as outlined in Section 6.0. The details of the study treatment will be documented in the eCRF and IMP accountability forms as applicable.

All study treatment related procedures will be performed in the hospital or clinic by qualified health care personnel. All instances of noncompliance and all resulting protocol deviations will be recorded by the monitors during the routine monitoring visits in the Monitoring Report.

6.0 TREATMENT OF PATIENTS

6.1 Drug Supply and Handling Procedures

6.1.1 Investigational Medicinal Product, APR-246

The IMP will be manufactured according to Good Manufacturing Practice (GMP), and labeled according to GCP, GMP and the national requirements for each site. The labels will comply with the legal requirements of the country. They will include storage conditions for the drug but no information about the study.

The IMP will be distributed in vials to the pharmacies of each participating study center. The APR-246 substance will be diluted in 0.9% sodium chloride solution at the appropriate concentration for infusion for each patient.

At the pharmacies, the IMP vials are to be stored at 2-8°C. At the pharmacies and at the study centers, the prepared APR-246 study product (diluted in sodium chloride solution) is to be stored at not more than 25°C. The infusion should be completed within 24 hours from the time of preparation (see Study Manual).

Detailed instructions on vial concentration, preparation and dispensing can be found in the pharmacy file.

6.1.2 Pegylated Liposomal Doxorubicin Hydrochloride

PLD will be provided from the pharmacy stock. The PLD bag used for administration will be labeled according to the local routines and regulatory requirements. The hospital will be responsible for ordering PLD. The manufacturer and batch numbers will be documented.

Please refer to the summary of product characteristics for further information on PLD.

6.2 IMP Accountability/Disposition of Clinical Trial Supplies

IMP accountability records will be maintained for all clinical trial supplies.

IMP accountability records will be kept at the pharmacy and at the study centers. The pharmacy must maintain accurate records demonstrating date and amount of IMP received, to whom and by who administered, and accounts of any IMP accidentally or deliberately destroyed.

The investigator is responsible for keeping records to ensure that:

- Deliveries of IMPs are correctly received and recorded by a designated person.
- Study medications are handled and stored safely and properly.
- Study medications are dispensed only to study patients in accordance with the protocol.
- All unused medication and empty containers are stored until they have been checked by the

study monitor.

- It is possible to reconcile records of all used and unused stocks as confirmed by the investigator's signature.

[figure not shown]
The IMP is the property of Aprea Therapeutics AB and must not be passed on to third parties. Any discrepancies between returned and expected returned IMP should be explained.

6.3 Main Study Treatment Administration

Starting within 28 days of registration, patients will receive a fixed dose of 4.5 g APR-246 (1.5 g of the dose during first 45 minutes followed by 3 g of the dose during 5 hours 15 minutes) on Days 1 to 4 with PLD 40 mg/m² on Day 4 (Figure 3). The PLD administration to be given on Day 4 only should commence 2 hours after the start of the APR-246 infusion.

Similarly for the following 28-day cycles, APR-246 will be administered on Days 1 to 4 with the PLD infusion on Day 4 starting 2 hours after the start of the APR-246 infusion.

Figure 3. Treatment Administration

Note: The entire dose should be given even if the infusion needs to be extended beyond a total time of 6 hours (e.g. due to slightly larger start volume in prefilled infusion bags).

APR-246 Treatment Duration

Treatment will be repeated every 28 days in the absence of disease progression or unacceptable toxicity. Supportive therapy, including growth factors, can be given as per institutional standard of care.

Pegylated Liposomal Doxorubicin Dosing

[figure not shown]
The dose of PLD will be calculated based on the body surface of the patients at 40 mg/m² as per standard practice at that hospital.

6.4 Sub-Study Treatment Administration

Starting within 28 days of registration, patients will receive a fixed dose of 4.5 g APR-246 in a 2-step infusion, starting with a loading dose given during first 45 minutes followed by slower infusion of the remainder of the dose, during 2 hours 15 minutes on Days 1 to 4, with PLD 40 mg/m² on Day 4 (Figure 4). The PLD administration to be given on Day 4 only should commence 2 hours after the start of the APR-246 infusion.

Similarly for the following 28-day cycles, APR-246 will be administered on Days 1 to 4 with the PLD infusion on Day 4 starting 2 hours after the start of the APR-246 infusion.

Figure 4. Treatment Administration in Sub-Study

Note: The entire dose should be given even if the infusion needs to be extended beyond a total time of 3 hours (e.g. due to slightly larger start volume in prefilled infusion bags).

APR-246 Treatment Duration

Treatment will be repeated every 28 days in the absence of disease progression or unacceptable toxicity. Supportive therapy, including growth factors, can be given as per institutional standard of care.

Pegylated Liposomal Doxorubicin Dosing

The dose of PLD will be calculated based on the body surface of the patients at 40 mg/m² as per standard practice at that hospital.

6.4.1 Sub-Study Doses and Infusion Times

[figure not shown]
Follow the flowchart for the Sub-Study (Figure 5), starting with 3 hr 4.5 g dose. Switch to 4 hr 4.5 g infusion or 4 hr 3.7 g infusion, as indicated, based on the occurrence of dose-limiting toxicities (DLTs).

DLTs include:

- Grade 4 thrombocytopenia lasting greater than 7 days
- Grade 4 neutropenia lasting greater than 7 days
- Other grade 4 hematological toxicities which last at least 5 days
- Grade 3 or 4 febrile neutropenia
- Grade 3 or greater non-hematological toxicities; these include grade 3 or greater diarrhea, nausea or vomiting despite adequate treatment which last greater than 3 days
- Patients who are unable to be dosed for more than 5 weeks from the planned start date of the next cycle due to toxicity

Please refer to Section 6.5 for dose modification procedures.

Figure 5. Sub-Study Flowchart

6.5 Dose Modifications for APR-246 due to Adverse Events During Infusion

If a patient has any clinical adverse event \geq grade 3 during the APR-246 infusion, the infusion should immediately be stopped. The type, severity and duration of the adverse event should be carefully assessed as well as the relationship to APR-246.

If the adverse event is considered to be unrelated to APR-246, the infusion may be resumed within 2 hours.

If the adverse event is considered to be related to APR-246, as long as all symptoms resolve to CTCAE Grade 1 or less within 2 hours, the infusion may be resumed.

In case of re-challenge, the infusion should resume at the same infusion rate (the same dose per time unit) as the initial infusion. If no symptoms occur during re-challenge, the infusion can continue until the whole dose is given and the treatment can continue according to the protocol.

If the same symptoms do occur or increase in severity during re-challenge the infusion should be stopped.

If the event lasts longer than 2 hours, then the remainder of the APR-246 infusion for that day should be discarded. If the patient has recovered sufficiently by the next day, the remainder of the planned course should be administered.

6.5.1 Main Study APR-246 Dose Reductions

After an adverse event considered as related, a single level dose reduction of APR-246 is allowed. Dose reductions are defined in Table 1. If there is a further need for a patient to have another dose reduction, this should be discussed with the Sponsor prior to any treatment decisions. The type, severity and duration of the symptoms, adverse event and infusion timings (start and stop) should be carefully documented in the patient's medical charts as per trial procedures.

Table 1. Dose Modifications of APR-246 in Main Study

Dose Modification	APR-246 Dose
Current Dose Level (DL)	APR-246 4.5 g 1.5 g (for first 45 minutes) + 3 g (for 5 hours 15minutes)
First dose reduction DL-1	APR-246 4.0 g 1.33 g (for first 45 minutes) + 2.67 (for 5 hours 15 minutes)
Second dose DL-2*	APR-246 3.5 g 1.16 g (for first 45 minutes) + 2.34 g (for 5 hours 15 minutes)

The rationale behind this dose reduction scheme is the steep relation between C_{max} and dose, e.g. the suggested 11.1% and 22.2% reductions in dose results in 19.4% and 33.4% lowering of the average C_{max}, respectively. See also Appendix III.

* Discuss with Sponsor and or medical monitor before implementing this reduction.

6.5.2 Sub-Study APR-246 Dose Reductions

After an adverse event considered as related, the infusion time may be extended to a total of 4 hours to achieve a reduced maximum blood concentration of APR-246. If a related adverse event occurs with the 4 hour infusion, APR-246 dose will be de-escalated. Dose reductions are defined in Table 2. If there is a further need for a patient to have another dose reduction, this should be discussed with the Sponsor prior to any treatment decisions. The type, severity and duration of the symptoms, adverse event and infusion timings (start and stop) should be carefully documented in the patient’s medical charts as per trial procedures.

Table 2. Dose Modifications of APR-246 in Sub-Study

Dose Modification	APR-246 Dose and Regimen
Starting Regimen, 3-hour infusion	APR-246 4.5 g 2.3 g (for first 45 minutes) + 2.2 g (for 2 hours 15minutes)
4-hour infusion	APR-246 4.5 g 2.0 g (for first 45 minutes) + 2.5 (for 3 hours 15 minutes)
4-hour infusion of reduced amount*	APR-246 3.7 g 1.6 g (for first 45 minutes) + 2.1 g (for 3 hours 15 minutes)

* Discuss with Sponsor and or medical monitor before implementing this reduction.

6.5.2.1 APR-246 Infusion and Systemic PLD Chemotherapy Delays

The Day 1 to 4 APR-246 administration, together with the Day 4 PLD chemotherapy, is to be regarded as one treatment cycle and must not be administered separately.

On Day 1, prior to APR-246 administration, the hematological status of the patient should be assessed. If the patient has any hematological AE that would prevent systemic chemotherapy administration on Day 4, the APR-246 infusion and systemic chemotherapy should be delayed until recovery.

If a patient has any AE on Day 2, 3 or 4 prior to the APR-246 infusion which, in the opinion of the Investigator, would prevent systemic chemotherapy administration, the remainder of the planned APR-246 administration should be stopped. Once the patient has recovered sufficiently to receive chemotherapy, the whole treatment cycle (consisting of Days 1-4 APR-246 and Day 4 chemotherapy) should be restarted as previously planned.

If APR-246 and/or systemic chemotherapy are delayed, the reasons for delay should be recorded in the eCRF.

6.5.3 Dose Modifications for PLD

For typical hematological and non-hematological AEs seen with PLD the dose modifications should be according to the current summary of product characteristics. However, if any AEs occur that are not typical or that are considered unusual, the Sponsor should be consulted prior to re-treating the patient.

If due to AEs the patient is unable to continue chemotherapy with PLD, the patient may continue monotherapy APR-246 if the following criteria are met:

- Latest radiological scans show evidence of response.
- Patient is evaluated as not having symptoms suggestive of progressive disease.
- The Investigator assessment is that APR-246 monotherapy is of continued benefit to the patient.
- APR-246 administration has been approved by the Sponsor.

6.5.4 Cardiac Safety Monitoring in Relation to Treatment With PLD

Whenever cardiomyopathy is suspected, i.e., the LVEF has substantially decreased relative to pretreatment values and/or LVEF is lower than a prognostically relevant value (e.g., < 45%), the benefit of continued therapy must be carefully evaluated against the risk of developing irreversible cardiac damage. Cardiology consultation is recommended. Local practice should be followed.

Previous clinical trial experience with PLD for the treatment of ovarian cancer has been summarized and may be a useful reference [18].

6.5.5 Action to be Taken in the Event of QT/QTc Prolongation

Although the risk of QT/QTc prolongation is considered to be very low, in the event of prolongation of the QT/QTc interval > 500 msec or an increase of > 60 msec over baseline, study treatment should be discontinued and appropriate close (continuous) ECG monitoring in a hospital setting should be initiated until the opinion of a cardiologist is obtained.

6.5.6 Treatment of APR-246-Related Adverse Events of the CNS

If a patient reports any clinical AE of any grade during the administration period of APR-246 that could be considered to originate from the CNS (e.g., dizziness, vertigo or nausea), then the following medications may be used (Table 3). Medications of a similar nature to reflect local practice may be used.

Table 3. Examples of Rescue Medications for Use With APR-246

Indication	Supportive Measure
CNS symptoms (treatment and prevention)	Prochlorperazine 10 mg orally tid ^a Start Day -1 prior to APR-246 administration
Persistent CNS symptoms	Cyclizine 50 mg IM

^a Prochlorperazine 10 mg orally tid (three times daily). To continue until end of Day 4 of the cycle. When used prophylactically for future treatment, start the day prior to the Day 1 administration of APR-246.

If during the infusion the patient continues to remain symptomatic intramuscular administration of cyclizine 50 mg should be considered.

6.6 Concomitant Treatment and Prohibited Medication

Patients are allowed to receive supportive care therapies (including cytokine growth factors) concomitantly during the trial.

No anti-cancer therapy other than that given in this clinical trial; no immunotherapy; no hormonal cancer therapy; no radiation therapy (except palliative); and no experimental medications are permitted during the trial. No PARP inhibitors are permitted after a beneficial response to study therapy.

Radiation therapy to index lesions should be avoided where possible; when deemed essential for patient well-being, the sponsor must be informed as the patient will become non-evaluable for endpoints assessed by RECIST, i.e. response rate and PFS.

Concomitant use of paracetamol-based compounds is allowed. However, caution should be taken when co-administering APR-246 with high doses of paracetamol (i.e., 4 g/24 h). Use of paracetamol must be terminated if any liver function tests increase above normal ranges.

Any disease progression that requires other specific antitumor therapy will be cause for discontinuation from the trial.

Anticoagulant Therapy: Patients who are taking warfarin may participate in this trial; however, it is recommended that prothrombin time (international normalized ratio [INR]) is monitored carefully at least once per week for the first month, then monthly if the INR is stable. Subcutaneous heparin is permitted.

Concurrent or procedural medications or therapy given to or taken by the patient will be recorded in the CRF along with the indication. All concomitant medication should be recorded for up to 30 days following the last protocol treatment. After this period, only relevant medication (e.g., medication in patients with treatment-related AEs) will be recorded in the CRF.

Both generic and trade names may be recorded. However, the generic name is generally preferred because of its specificity, whereas trade names are preferred for combination products.

The potential interaction of APR-246 with other medicinal products has not been investigated.

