9.1 Sample Size

The aim is to determine the preliminary efficacy of APR-246 with PLD. The endpoint of interest is the ORR as defined in Section 8.3.2.2.

A two stage design is used to test the null hypothesis that the true response rate of APR-246 in combination with PLD is $\leq 10\%$ versus the alternative that the true response rate is $\geq 30\%$. In the first stage, 16 patients will be assessed for response; if ≤ 1 response is seen in these 16 patients the study will be curtailed for futility. Otherwise the study will continue and a further 9 patients will be entered, for a total of 25 evaluable patients. If ≥ 5 responses are observed in these 25 patients, the null hypothesis will be rejected in favor of the alternative. This design provides 90.3% power and a 1-sided alpha of 9.5%.

Sub-Study Sample Size:

The aim is to determine the safety, tolerability and efficacy of a shorter infusion of APR-246 with PLD. The endpoint of interest is safety.

At one of the shorter infusion levels (3 hr 4.5 g, 4 hr 4.5 g, or 4 hr 3.7 g) if there are 0 or 1 out of 6 patients with DLTs across the first 6 patients, then an additional 8 patients will be treated for an initial total of N=14. If 0 or 1 out of 14 responses are seen, then recruitment will cease. If 2 or more out of 14 responses are seen, a further 11 patients will be recruited for a total of N=25. Observance of 5/25 responses will result in rejection of the null hypothesis. The design carries 89% power and a 1-sided type I error of 9.1% to test the null hypothesis that the true response rate is $\leq 10\%$ vs the alternative that the true response rate is 30%.

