9.3 Analysis Populations

The following populations will apply:

Safety Evaluable Population: All patients who received study medication (APR-246 or PLD) will be considered evaluable for safety regardless of the duration of treatment. This population will be used

to summarize all safety parameters.

Efficacy Evaluable Population: All patients with pretreatment measurable disease by RECIST 1.1 who have at least one radiographic assessment after pretreatment or discontinue study medication early due to disease progression and have a p53 mutation will be considered evaluable for efficacy. The efficacy-evaluable population will be the primary analysis population for efficacy.

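### Section 6.6 makes a patient with an irradiated index lesion non-evaluable for response rate and PFS, while the primary efficacy population in 9.3 can keep her, so the ORR denominator is not settled

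*Combined protocol and SAP*

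**What the plan says.** - **Protocol 6.6 (concomitant treatment).** Palliative radiotherapy is the one exception to the ban on radiation during the trial. Irradiating index lesions is to be avoided where possible. When it is judged essential, "the sponsor must be informed as the patient will become non-evaluable for endpoints assessed by RECIST, i.e. response rate and PFS". The subject of the sentence is the patient and the endpoints, not later scans. It gives no time limit and no exception for a response already confirmed or a non-response already assessed.
- **Protocol 9.3 (analysis populations).** The Efficacy Evaluable Population is the primary population for efficacy. It takes patients with measurable disease and a p53 mutation "who have at least one radiographic assessment after pretreatment or discontinue study medication early due to disease progression". Radiotherapy is not mentioned.
- **Protocol 9.1 (sample size).** With one response or none, "response is seen in these 16 patients the study will be curtailed for futility". Otherwise "a further 9 patients will be entered, for a total of 25 evaluable patients", and the null is rejected with five or more responses. The word evaluable is attached to the total of 25. The first 16 are described as patients assessed for response.
- **Elsewhere.** Sections 8.3.2.2 and 8.3.3 (best response and confirmation) and 9.4.1 (ORR and PFS analysis) give no radiotherapy rule. Section 5.3 provides for replacement only of patients withdrawn before completing the first cycle. Section 9.2 defers detail to an SAP to be written before data lock, and the combined document contains none.

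**The concern.** Consider two patients. One has stable disease at the end of Cycle 2 and then needs radiotherapy to a painful target mass. The other has a confirmed partial response and is irradiated months later. Section 9.3 keeps both in the ORR, one as a non-responder and one as a responder. Section 6.6, taken at its word, drops both.

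Irradiation of a target lesion happens after baseline and may be related to how the patient is doing on treatment. Excluding patients for it can therefore shift the response rate in a single-arm trial whose conclusion turns on five responses in 25. Losing non-responders makes an inactive regimen look better. Losing responders makes an active one look worse. In an open-label trial, a choice between the two sections made shortly before data lock would be made with the responses known. PFS has the same gap: non-evaluable could mean excluded or censored, and 9.4.1 does not say which.

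**Working it through.** **1. Reproduce the stated design.** Inputs from 9.1: null rate 10%, alternative 30%, n1 = 16, continue with at least 2 responses, n = 25, reject with at least 5. The probability of passing at a true rate p is

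P(p) = Σ over x ≥ 2 of Pr[Bin(16, p) = x] × Pr[Bin(9, p) ≥ max(0, 5 − x)].

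| Stage-1 responses | p = 0.10 | p = 0.30 |
|---|---|---|
| 2 | 0.2745 × 0.0530 = 0.0145 | 0.0732 × 0.5372 = 0.0393 |
| 3 | 0.1423 × 0.2252 = 0.0321 | 0.1465 × 0.8040 = 0.1178 |
| 4 | 0.0514 × 0.6126 = 0.0315 | 0.2040 × 0.9596 = 0.1958 |
| 5 or more | 0.0170 × 1 = 0.0170 | 0.5501 × 1 = 0.5501 |
| Sum | 0.0951 | 0.9030 |

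This agrees with the stated 9.5% and 90.3%.

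**2. Non-responders removed, 25 evaluable still reached.** Let s be the share of all patients removed, all of them non-responders. The rate among those left is p′ = p / (1 − s), and P(p′) follows from step 1. The documents give no radiotherapy frequency, so s is assumed.

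| s | p′ when p = 10% | Chance of passing |
|---|---|---|
| 0 | 10.0% | 9.5% |
| 4% | 0.10/0.96 = 10.4% | 10.9% |
| 8% | 0.10/0.92 = 10.9% | 12.5% |
| 12% | 0.10/0.88 = 11.4% | 14.3% |

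In a trial of 25, 4% is one patient.

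**3. Responders removed.** One confirmed responder dropped without refilling turns 5/25 (20.0%, one-sided 90% Clopper-Pearson lower limit 10.06%, reject) into 4/24 (16.7%, lower limit 7.5%, fewer than five responses). If a share q of responders is removed and the places are refilled, p′ = p(1 − q) / (1 − pq). At p = 30%:

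- q = 5%: 0.285/0.985 = 28.9%, power 88.3%.
- q = 10%: 0.27/0.97 = 27.8%, power 85.8%.

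Removal unrelated to response leaves the expected rate unchanged.

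**4. No refilling.** Dropping one non-responder turns 5/25 into 5/24 (20.8%, lower limit 10.5%). If a place is lost regardless of response and five responses are still required among 24, the same formula with 8 patients in stage 2 gives alpha 8.3% and power 88.4%. The stated operating characteristics no longer apply in this case either.

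**5. After the fix.** Patients stay in the denominator, and a response not confirmed before radiotherapy counts as non-response. If a share q of responders is affected, the rate is p(1 − q), which cannot exceed p, so type I error cannot exceed 9.5%. Power is 90.3% at q = 0, 87.3% at q = 5% (rate 28.5%) and 83.7% at q = 10% (rate 27.0%). These shares are also assumed.

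**The case against.** The strongest reply is that 9.3 is the named primary population and already settles the matter. On this view 6.6 is a medication section explaining why the sponsor must be told, and a patient who becomes non-evaluable does so only from that point on. Section 8.3.2.2 defines best response as the best recorded up to progression, and Tables 5 and 7 treat non-evaluable as a status at a time point. A confirmed partial response would then stand, and stable disease would remain stable disease. This is a sensible reading and close to the fix. But 6.6 speaks of the patient and of whole endpoints, and no section says which text prevails. What stands is that actual removal of patients from the ORR is not established. The ambiguity is.

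Other points also stand:

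- Exposure is probably limited. Section 6.6 discourages index-lesion radiotherapy, and progression requiring other antitumor therapy already leads to discontinuation.
- Refilling is an inference from the count of 25 evaluable patients. The only explicit replacement rule, in 5.3, does not reach these patients.
- A reader might infer that the clause always inflates the ORR. It does not, as step 3 of the working shows.
- A reader might infer that the stage-1 count is defined in evaluable patients. Section 9.1 says only that the 16 are assessed for response, and the patient with stable disease at Cycle 2 has been assessed. The stage-1 denominator still needs stating, but 6.6 does not plainly alter it.

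**Conclusion.** The conflict between 6.6 and 9.3 is real and unreconciled in the documents, and it reaches the primary endpoint. A patient irradiated after a post-baseline scan is non-evaluable under one section and in the primary population under the other. With a threshold of five in 25, one reclassification can change the decision.

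The type I error figures of 10.9%, 12.5% and 14.3% are illustrations. They require an assumed removal frequency, every removed patient being a non-responder, and refilling to 25. Removing confirmed responders lowers ORR and power instead. The documents fix neither the net direction nor the size. They do not support concluding that the stated alpha and power are wrong, because both reproduce, nor that patients will in fact be removed. The case for acting is that the primary denominator should not depend on which section is read, and that the repair is small.

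**What to change.** - **6.6:** replace the patient-level non-evaluable statement, for both response rate and PFS, with a cross-reference to 9.3 and 9.4.1. Say that index lesion means target lesion as in 8.1.3, if that is intended.
- **9.3:** state that patients who otherwise qualify stay in the ORR denominator at stage 1 and at the final analysis. They count as responders only if CR or PR was confirmed under 8.3.3.1 before the first radiotherapy to a target lesion, and otherwise as non-responders. Later scans do not contribute to best response.
- **9.4.1:** state that they stay in the PFS analysis, under a stated event or censoring rule.

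**Cost.** The change is a few sentences. The ORR may be slightly lower, and power falls where radiotherapy comes before a response is confirmed (step 5 of the working). The rule also needs the radiotherapy start date and the irradiated lesion. Section 6.6 requires therapy and its indication to be recorded but does not say that these two items are, so the CRF must be checked and extended if necessary. Whether radiotherapy is given is not affected.
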